8.4 Procedure for Adverse Event Reporting

8.4.1 Serious Adverse Events (SAEs)

All SAEs that occur during the designated study period from randomization through EOS must be reported using study specific SAE Report Form within 24 hours of awareness of the event. Each SAE must also be recorded on the source documents and on the appropriate page of the eCRF.

The Investigator should provide any follow-up information for the event to the Sponsor on an updated SAE Report Form as soon as it becomes available. The Sponsor will contact the Investigator, if necessary, to clarify any of the event information or request additional information.

If the Investigator is notified of a SAE that occurs post-study period, that he or she wishes to report to the Sponsor (eg, an event suspected to be causally related to investigational product), the event should be reported through the process described above.

Where appropriate, if required by local regulations or procedures, the Investigator should report these events to the Institutional Review Board (IRB)/Ethics Committee (EC) and/or national regulatory authority in addition to the Sponsor.

8.4.2 Nonserious AEs

All nonserious AEs that occur during the designated study period from randomization through EOS must be assessed and recorded on the source documents and eCRF, regardless of causal relationship to the investigational product.

8.4.3 Special situations

8.4.3.1 Medication Errors

Medication errors (e.g, wrong dose concentration, wrong treatment, wrong regimen, wrong injection site), with or without an associated AE, will be reported as a protocol deviation ([Section 12.3](#)). Medication errors and an associated SAE will be recorded in the eCRF and also reported to the Sponsor as described in [Section 8.4.1](#). Medication errors and an associated non-serious AE will be recorded in the eCRF as described in [Section 8.4.2](#).

8.4.3.2 Pregnancy

Occurrences of pregnancy/lactation exposure in a study subject from the time of Day 1 through EOS must be reported to the Sponsor within 24 hours using the Pregnancy Exposure Report Form.

In cases where a pregnancy/lactation exposure occurs with a SAE, the SAE Report Form should be used to report the SAE and the Pregnancy Exposure Report Form should be used to report the pregnancy/lactation exposure.

When a pregnancy occurs without any concurrent SAE, the Pregnancy Exposure Report Form must be submitted alone.

The pregnancy should be followed up to determine outcome, including spontaneous or voluntary termination, details of the birth, and the presence or absence of any birth defects, congenital

abnormalities, or maternal and/or newborn complications. Newborns should be followed for 12 months.

8.5 Expectedness

8.5.1 Expectedness Determination

Novartis Safety Department will be responsible for determining whether an AE is expected or unexpected for the purpose of SUSAR reporting. An AE will be considered unexpected if the nature, severity, or frequency of the event is not consistent with the safety information previously described for the investigational product in the current/approved version of the Inclisiran Investigator's Brochure.

8.6 Study Stopping Criteria

8.6.1 Independent Data Monitoring Committee (IDMC) Stopping Rules

The IDMC will use all available evidence and its collective judgment to make a recommendation to continue, stop, or amend the study at any of its reviews during the double blind and open label part of the study. Any statistical considerations are not a substitute for the committee's medical, scientific, or statistical expertise. Details will be provided in the IDMC charter.

8.6.2 Sponsor Discontinuation Stopping Criteria

The Sponsor will review data on an ongoing basis and may, on discussion with the IDMC terminate the study for any clinically significant drug related safety signal (eg. serious hypersensitivity reactions or drug induced liver injury, etc).

Premature termination of a study may also occur because of a regulatory authority decision, change in opinion of the IRB/EC, drug safety problems, or at the discretion of the Sponsor. In addition, the Sponsor retains the right to discontinue development of inclisiran at any time.

If a study is prematurely terminated or discontinued, the Sponsor will promptly notify the investigator. After notification, the investigator must contact all participating subjects and the hospital pharmacy (if applicable) within 30 days of the notification. Final study visits should occur within 30 days of subject contact. As directed by the Sponsor, all study materials must be collected and all eCRFs completed to the greatest extent possible.

The Sponsor will inform the health authorities and the IRBs/EC that the study has been stopped and the reasons for doing so, within the locally applicable timelines.

9 Data Collection

An electronic data capture (EDC) system which is 21 CFR Part 11 compliant will be used for this study. All users will be trained on the technical features of the EDC as well as the content of the eCRF by qualified personnel prior to gaining access to the EDC. A UserID/Password will be granted after training. This ID is not to be shared amongst the study staff. All users must have a unique account to enter or review data. The eCRF should be filled out by the site 3 days after each

visit. It is not expected that the eCRF will serve as source for any data collected in this study. If there is a reason for a site to do so, it must be approved by Sponsor and documented in the site files.

Prior to the database being locked, the investigator or designee will review, approve and sign/date each completed eCRF. This signature serves as attestation of the Investigator's responsibility for ensuring that all data entered into the eCRF are complete, accurate and authentic. After the end of the study, a copy of the data will be provided to the site. This copy will contain the final data, an audit trail of activity on the data, and any queries and answers that were posted for data clarification. For this study, the EOS will be defined as the last visit of the last subject.

10 Statistical Plan

This study will be a Phase III, two-part (double-blind placebo-controlled/open-label) multicenter study to evaluate safety, tolerability, and efficacy in subjects with HoFH. This study has two sequential parts:

- Part 1: 6-month double-blind period in which subjects will be randomized to receive either inclisiran or placebo
- Part 2: 18-month open-label follow-up period; placebo-treated subjects from Part 1 will be transitioned to inclisiran and all subjects will participate in an open-label follow-up period of inclisiran only

The study will be a multicenter, international study. A separate Statistical Analysis Plan (SAP) document will provide more detailed specifications in data analysis and presentation.

10.1 Sample Size

The sample size calculation was performed with the hypothesis that the difference of mean percent change from baseline to Day 150 between inclisiran and placebo will be >20% (20% standard deviation) in subjects with HoFH when treated with inclisiran. The sample size of at least 45 subjects (randomized 2:1 to inclisiran : placebo), with at least 30 subjects in the inclisiran arm, will provide >80% power to detect a 20% reduction of LDL-C levels from baseline in the inclisiran group compared to that in the placebo at one-sided significance level of 0.025 based on two-sample t-test.

10.2 Randomization

Randomization should only occur once subject eligibility is confirmed and will be conducted via an automated interactive response technology (IRT) to assign subjects to blinded investigational product at 2:1 ratio to inclisiran versus placebo. Each subject will receive SC injections of blinded inclisiran or placebo on Day 1 and Day 90. The inclisiran-treated subjects will receive a third dose of inclisiran administered on Day 270 and subsequent doses on Day 450 and Day 630. The placebo-treated subjects from Part 1 will transition to an open-label, single arm follow-up period of inclisiran only; placebo-treated subjects will receive their first dose of inclisiran on Day 180 and then subsequently receive a dose of inclisiran on Day 270, Day 450, and Day 630.

10.3 General Statistical Considerations and Definitions

10.3.1 General Statistical Methods

All study-collected data will be summarized by treatment group using descriptive statistics, graphs, and/or raw data listings. Descriptive statistics for continuous variables will include number of subjects (n), mean, standard deviation (SD), median, quartiles (Q1 and Q3), minimum (min) and maximum (max) values. Analysis of categorical variables will include frequency and percentage.

10.3.2 Analysis Population

The following populations will be used for data analyses and/or presentation.

10.3.2.1 Intent-to-Treat (ITT) Population

All subjects randomized into the study will comprise the ITT population. Treatment classification will be based on the randomized treatment. The ITT population will be used as the primary population for efficacy.

10.3.2.2 Modified Intent-to-Treat (mITT) Population

All randomized subjects who receive at least one dose of investigational product and have both the baseline and the 150 day follow-up LDL-C assessment will comprise the mITT population. Treatment classification will be based on the randomized treatment. This population will be used to confirm the efficacy.

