Unless specified otherwise, the ITT will be the primary analysis population for efficacy analysis and Safety population will be the primary population for safety analysis in this study. mITT population will be used to confirm the efficacy.

Statistical Analysis:

Statistical comparisons will only be performed for the Part 1 of the study. The statistical analysis for study Part 2 is descriptive.

Summary statistics for continuous variables will include the number of subjects, mean, median, standard deviation or standard error, minimum and maximum. For categorical variables, the frequency and percentage will be given.

The primary endpoint is the percent change from baseline in LDL-C following 150 days of treatment.

The primary analysis will be conducted using ANCOVA model based on the multiply imputed datasets (100 total) - Washout based approach. The ANCOVA model will include the fixed effect of treatment group (Inclisiran or placebo) and baseline LDL-C as a covariate. Treatment effects from these 100 ANCOVA analyses will then be combined using Rubin's method. The difference between treatment groups in mean change from baseline to Day 150 in LDL-C and corresponding two-sided 95% confidence interval will be provided. The p value for testing equal mean change from baseline to Day 150 in LDL-C will also be provided. For the key secondary endpoints, the efficacy analyses will be similar to the primary analysis of the primary efficacy endpoint, the ANCOVA model will be used on the multiply imputed datasets (100 total) - Washout based approach. Treatment effects from these 100 ANCOVA analyses will then be combined using Rubin's method.

Additionally sensitivity analysis including MMRM on imputed data using PMM and without imputation will be performed for both primary and key secondary endpoints except for the endpoint of $\geq 30\%$ LDL-C reduction from baseline to Day 150, which will be analyzed using the logistic regression model with treatment as the effect.

This study is sufficiently powered for the hypothesis testing in the primary and key secondary endpoints, all other endpoints are supportive hence no adjustment for multiplicity is planned.

Safety summaries will include the incidence of AEs, summaries of laboratory parameters, vital signs, and ECGs.

Table of contents

Protocol Synopsis	2
Table of contents.....	8
List of tables.....	12
List of figures.....	12
List of abbreviations	13
Amendment 1 (08-Oct-2020).....	16
1 Introduction.....	26

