HoFH	homozygous familial hypercholesterolemia
HR	heart rate
hsCRP	high sensitivity C-reactive protein
IB	Investigator's Brochure
ICH	International Conference on Harmonisation of Technical Requirements for Registration of Pharmaceuticals
IDMC	Independent Data Monitoring Committee
IFN- γ	interferon-gamma
IL6	interleukin 6
INR	International normalized ratio
IRB	Institutional Review Board
IRT	Interactive Response Technology
ITT	intent-to-treat
IV	Intravenous
L	Liter(s)
LDL	low density lipoprotein
LDL-C	low density lipoprotein cholesterol
LDLR	low density lipoprotein receptor
Lp(a)	lipoprotein(a)
<hr/>	
MCH	mean cell hemoglobin
MCHC	mean corpuscular hemoglobin concentration
MCV	mean corpuscular volume
MDCO	The Medicines Company
MedDRA	Medical Dictionary for Regulatory Activities
mg	Milligram
MI	myocardial infarction
MITT	Modified intent-to-treat
mL	milliliter(s)
mmHg	millimeters of mercury
mmol	Millimole
MMRM	mixed-effect models for repeated measures
mRNA	messenger ribonucleic acid
NYHA	New York Heart Association
PCS	potentially clinical significant
PCSK9	proprotein convertase subtilisin/kexin type 9
PD	pharmacodynamic
PEF	peak expiratory flow
PK	pharmacokinetic
PMM	Pattern-Mixture Model

PT	prothrombin time
RISC	RNA-induced silencing complex
RNA	ribonucleic acid
RNAi	ribonucleic acid interference
SAE	serious adverse event
SAP	Statistical Analysis Plan
SC	Subcutaneous
SD	standard deviation
siRNA	small interfering ribonucleic acid
SUSAR	suspected unexpected serious adverse reaction
$t_{1/2}$	terminal half-life
TBIL	total bilirubin
TC	total cholesterol
TEAE	treatment emergent adverse event
TNF- α	tumor necrosis factor-alpha
TTR	target transthyretin
ULN	upper limit of normal
US	United States
VLDL-C	very low density lipoprotein cholesterol
WHO	World Health Organization

Amendment 1 (08-Oct-2020)

Amendment rationale

The first subject for this trial was randomized in Feb 2019 and enrollment was completed in Sep 2019 (with 56 subjects enrolled). Part 1 (double-blind phase) of the trial was completed on 02-Mar-2020, when the last subject completed the Day 180 visit and treatment allocation was unblinded. At time of this amendment, 51 subjects are still on study treatment.

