10.4.3 Efficacy Analysis

This study is sufficiently powered to show the effect in the primary and key secondary endpoints, all other secondary [REDACTED] endpoints are supportive hence statistical testing on all other secondary [REDACTED] endpoints will be performed only if the null hypothesis on primary and the key secondary endpoints are rejected. No adjustment for multiplicity is planned among the other secondary [REDACTED] endpoints.

The ITT population will be the primary population for the efficacy analysis. Efficacy analysis may also be performed for the mITT population as supportive analysis.

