10.4.3.1 Primary Efficacy Endpoints

The primary efficacy endpoint is percent change from baseline to Day 150 in LDL-C.

The primary analysis will be conducted using ANCOVA model based on the multiply imputed datasets (100 total). The ANCOVA model will include the fixed effect of treatment group (Inclisiran or placebo) and baseline LDL-C as a covariate. Treatment effects from these 100 ANCOVA analyses will then be combined using Rubin's method. The difference between treatment groups in mean change from baseline to Day 150 in LDL-C and corresponding two-sided 95% confidence interval will be provided. The p-value for testing equal mean change from baseline to Day 150 in LDL-C will also be provided.

The missing data imputation for primary analysis will be the Washout-model-based approach. The washout model can be thought of as a modified control-based Pattern-Mixture Model (PMM) that

will be used to explore the possibility of data missing not at random (MNAR) for subjects who discontinued the study early.

Sensitivity analysis for the primary efficacy endpoint will use Wilcoxon rank-sum test, a nonparametric analysis method, as well as the two-sample t-test.

Also, we will perform sensitivity analyses to explore the dropout pattern and its possible impact on treatment comparisons in order to support the robustness of the conclusion drawn from the primary analysis using data up to Day 180. Pattern-Mixture Model (PMM) will be used to check the robustness when data missing not at random (MNAR) for subjects who discontinued study treatment. A control-based pattern-mixture model will be utilized. Multiple imputation will be used to account for uncertainty in the imputation process and results from a Mixed-effects Model for Repeated Measures (MMRM) on the imputed datasets will be combined using Rubin's method. Furthermore, a tipping point analysis will be performed to search for the tipping point that reverses the study conclusion. In addition, an analysis based on a Mixed-effects Model for Repeated Measures (MMRM) without multiple imputation will be performed.

The primary analysis and sensitivity analyses will be performed on both ITT and mITT populations. Details of the sensitivity analysis specified above will be in the SAP.

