10.4.3.2 Secondary Efficacy Endpoints

For the first four key secondary endpoints, the following efficacy analyses will be performed on the ITT and mITT populations:

- Similar to the primary analysis of the primary efficacy endpoint, the ANCOVA model will be used on the multiply imputed datasets (100 total) – Washout based approach. Treatment effects from these 100 ANCOVA analyses will then be combined using Rubin's method.
- MMRM model will be used on the multiply imputed datasets (100 total) – PPM based imputation. Treatment effects from these 100 ANCOVA analyses will then be combined using Rubin's method
- Analysis based on a Mixed-effects Model for Repeated Measures (MMRM) without multiple imputation will be performed.

For the key secondary endpoint of $\geq 30\%$ LDL-C reduction from baseline to Day 150, a logistic regression model with treatment as the effect will be used, and the odds ratio and its 95% confidence interval will be provided. The multiply imputed datasets created from both the washout model and the control-based PMM will be utilized in this analysis.

For the other secondary endpoints specified in [Section 3.4](#), generally descriptive and graphical summaries by treatment group will be presented for the ITT population. The two-sided 95% confidence interval may be provided for continuous variables based on the MMRM model. Odds ratio and 95% confidence interval may be provided for binary variables. Nominal p-values may be provided when applicable. Details of the analyses for the secondary endpoints are specified in the SAP.

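### Does requiring an observed Day 150 LDL-C for the mITT set undermine the missing-data analyses ordered on it?

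*Protocol*

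**What the plan says.** Section 10.3.2.2, and the Synopsis in the same terms, defines mITT as randomized subjects with at least one dose who "have both the baseline and the 150 day follow-up LDL-C assessment will comprise the mITT population". The primary variable is the same measurement: "The primary efficacy endpoint is percent change from baseline to Day 150 in LDL-C" (section 10.4.3.1). The primary model uses no other visit: "The ANCOVA model will include the fixed effect of treatment group (Inclisiran or placebo) and baseline LDL-C as a covariate". It is fitted to 100 datasets imputed by the washout model. Section 10.3.4 imputes a value only where one is missing, up to Day 180. Section 10.4.3.1 adds a control-based pattern-mixture analysis with MMRM, a tipping-point search, an MMRM without imputation, a Wilcoxon test and a t-test.

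On which populations these are run, the text varies:

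- Synopsis, Study Population: "mITT population will be used to confirm the efficacy". Section 10.3.2.2 says the same.
- Section 10.4.3: "Efficacy analysis may also be performed for the mITT population as supportive analysis".
- Section 10.4.3.1: "The primary analysis and sensitivity analyses will be performed on both ITT and mITT populations".
- Section 10.4.3.2, for the first four key secondary endpoints: "the following efficacy analyses will be performed on the ITT and mITT populations".

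The Synopsis and sections 10.3.2.1 and 10.4.3 all name ITT as the primary efficacy population.

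**The concern.** Two things look wrong. First, mITT selects subjects on something seen only after randomization, namely whether the primary outcome was obtained. It is a Day 150 completer set. Ordering multiple imputation and a tipping-point search of Day 150 LDL-C on it orders procedures with nothing to act on. A table headed as washout-imputed or tipping-point, produced on mITT, could be taken as evidence that the LDL-C result withstands missing data, when every subject with missing data has been removed. Second, a reader may ask whether the mITT results are required confirmation or optional support. At stake would be how far agreement between ITT and mITT can be relied on in the report.

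**Working it through.** **The plan's own figure.** Section 10.1 claims power above 80% with 30:15 subjects, difference 20, SD 20 and one-sided alpha 0.025. The standard error is 20 × √(1/30 + 1/15) = 6.32 and the noncentrality is 20/6.32 = 3.16. On 43 degrees of freedom this gives 87.1% power, so the claim reproduces. Nothing below depends on it.

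**Is the collapse real?**

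1. Inputs to the primary ANCOVA: Day 150 LDL-C, baseline LDL-C and treatment (section 10.4.3.1).
2. Condition for mITT membership: baseline and Day 150 LDL-C both present (section 10.3.2.2).
3. Values to impute in mITT for this model: 0. The 100 fits are identical, so the between-imputation variance is B = 0.
4. Rubin's total variance is W + (1 + 1/100) × B, which reduces to W, the complete-case variance.
5. The tipping-point shift is added to imputed values. There are none, so the estimate cannot move.

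One simulated trial shows this. Assumptions: 37 inclisiran and 19 placebo subjects (56 enrolled, 2:1), true difference −20, SD 20, Day 150 missing for 4 inclisiran subjects and 1 placebo subject, placebo-based imputation.

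| Shift added to imputed inclisiran values | ITT estimate (SE) | mITT estimate (SE) |
|---|---|---|
| 0 | −16.7 (5.75) | −19.3 (5.23) |
| 20 | −14.6 (6.32) | −19.3 (5.23) |
| 50 | −11.3 (7.65) | −19.3 (5.23) |
| 100 | −5.9 (10.54) | −19.3 (5.23) |
| 200 | +4.9 (17.27) | −19.3 (5.23) |

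For ITT at shift 0, W = 30.16 and B = 2.92, so SE = √(30.16 + 1.01 × 2.92) = 5.75. For mITT, W = 27.31 and B = 0, so SE = √27.31 = 5.23, exactly the complete-case ANCOVA.

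The ITT column shows the tool working where it matters. The ratio of estimate to SE is −16.7/5.75 = −2.90, then −14.6/6.32 = −2.31, then −11.3/7.65 = −1.48. In this example the tipping point therefore lies between shifts of 20 and 50.

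**How far could ITT and mITT differ?** The protocol gives no Day 150 missing rate, so this is illustration only. If k of 37 inclisiran values are missing, imputed at placebo level, and missingness is unrelated to outcome, the expected ITT difference is 20 × (1 − k/37).

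| k missing | Expected ITT | Expected mITT | Gap | ITT between-imputation variance (1,000 simulated trials) |
|---|---|---|---|---|
| 2 | 18.9 | 20 | 1.1 | 0.78 |
| 4 | 17.8 | 20 | 2.2 | 1.70 |
| 6 | 16.8 | 20 | 3.2 | 2.81 |

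Amendment 1 reports 51 of 56 subjects still on treatment in October 2020, so 5 were off treatment across both arms. That is not a count of missed Day 150 visits. Section 4.5.1 asks subjects who stop study medication permanently to keep attending.

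**Would a rewrite change a result?** Replace the washout ANCOVA on mITT by an observed-data ANCOVA on the same subjects. By steps 3 and 4 the estimate and standard error are the same. Membership and every ITT analysis are untouched.

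**The wording on the role of mITT.** Section 10.4.3 is the general paragraph for all efficacy endpoints and uses *may*. Section 10.4.3.1 (primary) and section 10.4.3.2 (first four key secondary) use *will*. For the other secondary endpoints section 10.4.3.2 names ITT alone. A general permission followed by specific instructions can be read together: the specific text governs the endpoints it names.

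**The case for a change.** The best case for a change is that the protocol itself fixes the population, the list of analyses and the instruction to run them on mITT. An SAP that follows it must produce empty analyses, and one that does not departs from the protocol. A finding of no tipping point in mITT could be reported as reassurance, and rewording costs almost nothing.

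The factual part stands: for Day 150 LDL-C the washout and tipping-point analyses add nothing in mITT, and the optional and mandatory verbs do differ. Three things weaken the rest.

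- The protocol asks mITT only to confirm efficacy. Section 10.4.3.1 gives the missing-data question to the pattern-mixture and tipping-point analyses, which have full force in ITT. Checking that the effect is present among subjects with no imputed Day 150 LDL-C is an ordinary secondary check, so no stated purpose fails.
- Not all the mITT work is empty. The pattern-mixture MMRM may still impute Day 90 or Day 180, and Apo-B, non-HDL-C or total cholesterol may be missing at Day 150. Section 7.2.1 also has two LDL-C methods at Day 150; if membership rests on one and the endpoint on the other, a few values could be imputed even for the primary endpoint. Withdrawing all imputation-based analyses from mITT would discard analyses that have content.
- Rewording is not free at this stage. Part 1 ended on 02-Mar-2020, "when the last subject completed the Day 180 visit and treatment allocation was unblinded". Changing the description of an analysis population after that date has to be recorded and explained, and here it would alter no estimate.

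**Conclusion.** The observation is correct but calls for no change. Provided membership and endpoint use the same LDL-C method, the washout ANCOVA on mITT is a complete-case ANCOVA, with 0 imputed Day 150 values and 0 between-imputation variance, and the tipping-point search there has no solution. The primary inference rests on ITT, where both analyses operate as intended. Under the assumed 37:19 split and 2 to 6 missing inclisiran values, the ITT estimate would be about 1 to 3 points smaller than the mITT one, so the decision rests on the more cautious figure. With no missing Day 150 values, the two sets would give the same LDL-C result. What remains is redundancy in a few supportive tables and a clerical mismatch between a general *may* and specific *will*. An analyst can deal with both by footnoting the mITT tables as Day 150 completers with nothing imputed for LDL-C. Following the plan as written still leads to a sound conclusion.
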